7.2.3.5.2 Local Laboratory Testing

Local laboratory testing will be used to determine subject eligibility and for all clinical decisions. The following tests will be performed by the local laboratory:

DSA Identification

Please see Section [7.2.2.1](#). DSA testing at the local laboratory is only required at screening. If it is anticipated that the local DSA results will not be available within the screening period, previously obtained local DSA results can be used to assess eligibility, if obtained after kidney transplant and between 30 days prior to the biopsy that is diagnostic of the qualifying AMR episode and the time of obtaining informed consent. In any instance, a screening local DSA test should be performed after obtaining informed consent. Additional DSA tests may also be done locally at other time points at the discretion of the investigator according to local standard of care.

Safety Laboratories

Safety local laboratory values including white blood cell (WBC) count and platelets from the local laboratory will be used to determine eligibility.

BUN, Creatinine and eGFR Calculation

BUN and Serum Creatinine will be tested locally at all protocol-required study visits, and creatinine can be tested outside of the protocol-required study visits at the discretion of the investigator as part of standard of care in order to calculate eGFR and assess pre-AMR and resolution of AMR for all AMR episodes (qualifying and recurrent).

Pre-AMR eGFR values are required for all episodes of AMR in order to assess eligibility for enrollment into the study and for re-treatment of recurrent AMR episodes occurring within the first 180 days after the qualifying biopsy. The eGFR_{MDRD} need to also be obtained at screening (or screening for retreatment), using the first creatinine value available after the qualifying (or recurrent) biopsy that is diagnostic for AMR. At screening, this will be used for the purpose of assessing AMR severity for stratification. Pre-AMR and Resolution of AMR eGFR values are also required for all AMR episodes when AMR resolution is assessed clinically. Otherwise, resolution can only be assessed through histopathology (see Section 7.2.2.3).

Clinical sites will calculate the eGFR, including the pre-AMR eGFR baseline for each episode of AMR as well as their clinical resolution, using the local serum creatinine results and the appropriate MDRD equation as follows:

For standardized (IDMS-calibrated) serum creatinine assays:

$$eGFR_{MDRD} = 175 \times (\text{standardized serum Cr})^{-1.154} \times (\text{Age})^{-0.203} \times [1.210 \text{ if Black}] \times [0.742 \text{ if female}] \times [0.808 \text{ if Japanese}]$$

For non-standardized (non-IDMS-calibrated) serum creatinine assays:

$$eGFR_{MDRD} = 186 \times (\text{serum Cr})^{-1.154} \times (\text{age})^{-0.203} \times [1.210 \text{ if Black}] \times [0.742 \text{ if female}] \times [0.808 \text{ if Japanese}]$$

eGFR is expressed in mL/min/1.73m², serum creatinine is expressed in mg/dL, and age is expressed in years.

Coagulopathy Panel

In the event that a subject experiences an unexplained clinically significant thrombotic or thromboembolic event (Section 8.2.4), a coagulopathy panel will be performed at the site's local laboratory when clinically feasible to obtain, which may include at the discretion of the investigator some of the following test parameters:

- Activated protein C resistance ratio
- Alpha 2 Antiplasmin functional
- Anti-phospholipid antibody
- Antithrombin III antigenic level
- Antithrombin III functional
- Factor V, VIII, IX, XI levels
- Homocysteine level
- Plasminogen Activator Inhibitor-1
- Protein C activity
- Protein C antigen
- Protein S activity
- Protein S antigen

7.2.3.6 Pregnancy Test

A urine pregnancy test and a confirming serum beta-HCG pregnancy test (central and local laboratories) will be performed on females of child-bearing potential at the Screening Visit, and a urine pregnancy test will be performed on females of child-bearing potential on Day 1 of each AMR episode prior to investigational product administration.

7.2.3.7 Electrocardiogram

A 12-lead ECG will be performed at the Screening visit and at any additional time during the study if clinically indicated per standard of care. Each ECG will include heart rate, RR Duration, PR duration, QT duration, QRS duration. QTcF will be programmatically derived. The investigator will be responsible for providing the interpretation for all ECGs in terms of clinical significance to the subject.

7.2.4 Others

7.2.4.1 Pharmacokinetic/Pharmacodynamic Assessments

Blood samples for the determination of plasma concentrations of functional and antigenic C1 INH and complement components C3a and C5a will be collected at time points shown in [Table 3](#). “Time of dose” is defined as the start of the investigational product infusion.

Of note, if plasmapheresis, plasma exchange, or immune adsorption treatments are performed on a dosing day, blood samples for pharmacokinetic/ pharmacodynamic testing will be obtained before the DSA reduction and sucrose-free IVIg treatments, as well as prior to investigational product administration (ie, post-DSA reduction treatment), and at time points relative to the start of the investigational product infusion, as outlined in [Table 3](#). The actual date and time of each sample collection will be recorded. Plasma samples for the determination of antigenic and functional C1 INH concentrations and complement C3a and C5a levels will be analyzed according to validated methodology.

In addition, plasma samples will be stored and may be used to investigate additional complement or cytokine levels that might correlate with response to treatment.

7.2.4.2 Health Outcomes and Outcomes Research Assessments

The validated quality of life EQ-5D-5L questionnaire will be administered to subjects at the time points on [Table 1](#) and [Table 2](#).

7.2.4.3 Healthcare Resource Utilization

Healthcare resource utilization will be assessed at the time points on [Table 1](#) and [Table 2](#).

8. ADVERSE AND SERIOUS ADVERSE EVENTS ASSESSMENT

8.1 Definition of Adverse Events, Period of Observation, Recording of Adverse Events

An AE is any untoward medical occurrence in a clinical investigation subject administered a pharmaceutical product and that does not necessarily have a causal relationship with this treatment. An AE can therefore be any unfavorable and unintended sign (including an abnormal laboratory finding), symptom, or disease temporally associated with the use of a medicinal (investigational) product, whether or not related to the medicinal (investigational) product (ICH Guidance E2A 1995).

All AEs and SAEs will be recorded from the time the informed consent is signed through 30 days after the last dose of investigational product regardless of relationship to investigational product. This includes events occurring during the screening period, regardless of whether or not investigational product has been administered. Following the 30-day capture period for all AEs and SAEs, only those AEs/SAEs deemed related to investigational product or other protocol-mandated procedures as well as the events of special interest regardless of relationship to investigational product (any thrombotic or thromboembolic event, any hypersensitivity reaction, any new episode of kidney allograft rejection [excluding AMR] - Section 8.1.4) will be collected during the long-term follow-up phase of the study. If the subject undergoes retreatment with investigational product for a new AMR episode, AEs and SAEs will be captured as described above for the treatment of the initial occurrence of AMR. Where possible, a diagnosis rather than a list of symptoms should be recorded. If a diagnosis has not been made, then each symptom should be listed individually. All AEs should be captured on the appropriate AE pages in the CRF and in source documents. In addition to untoward AEs, unexpected benefits outside the investigational product indication should also be captured on the AE CRF.

All AEs must be followed to closure (the subject's health has returned to his/her baseline status or all variables have returned to normal), regardless of whether the subject is still participating in the study. Closure indicates that an outcome is reached, stabilization achieved (the investigator does not expect any further improvement or worsening of the event), or the event is otherwise explained. When appropriate, medical tests and examinations are performed so that resolution of event(s) can be documented.

8.1.1 Severity Categorization

The severity of AEs must be recorded during the course of the event including the start and stop dates for each change in severity. An event that changes in severity should be captured as a new event. Worsening of pre-treatment events, after initiation of investigational product, must be recorded as new AEs (for example, if a subject experiences mild intermittent dyspepsia prior to dosing of investigational product, but the dyspepsia becomes severe and more frequent after first dose of investigational product has been administered, a new AE of severe dyspepsia [with the appropriate date of onset] is recorded on the appropriate CRF).

The medical assessment of severity is determined by using the following definitions:

Mild: A type of AE that is usually transient and may require only minimal treatment or therapeutic intervention. The event does not generally interfere with usual activities of daily living.

Moderate: A type of AE that is usually alleviated with specific therapeutic intervention. The event interferes with usual activities of daily living, causing discomfort but poses no significant or permanent risk of harm to the research subject.

Severe: A type of AE that interrupts usual activities of daily living, or significantly affects clinical status, or may require intensive therapeutic intervention.

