### 11.1 Adverse Events

Adverse events will be coded using the Medical Dictionary for Regulatory Activities (MedDRA)

Adverse events and SAEs will be recorded from the time the informed consent is signed through 30 days after the last dose of investigational product regardless of relationship to investigational product. This includes events occurring during the screening period, regardless of whether or not investigational product has been administered. Following the 30-day capture period for all AEs and SAEs, only those AEs/SAEs deemed related to investigational product or other protocol mandated procedures will be collected during the long-term follow-up phase of the study. If the subject undergoes retreatment with investigational product for a new AMR episode, AEs and SAEs will be captured as described above for the treatment of the initial occurrence of AMR. In addition, the following events of special interest, both serious and non-serious, will be closely monitored and reported to Shire GDS via SAE form throughout the study, regardless of relationship to investigational product: any thrombotic or thromboembolic event, any hypersensitivity reaction, any new episode of kidney allograft rejection (excluding AMR), and any kidney allograft failure.

An adverse event that increases in severity will be captured as a new event. Worsening of pre-treatment events, after initiation of investigational product, will be recorded as new AE. An AE (classified by preferred term) that occurs during the study will be considered a treatment-emergent AE (TEAE) if:

- it has a start date and time on or after the first dose of investigational product, or
- it has a start date and time before the date and time of the first dose of investigational product, but increases in severity on or after the date and time of the first dose of investigational product.

If more than 1 AE with the same preferred term is reported before the date and time of the first dose of investigational product, then the AE with the greatest severity will be used as the benchmark for comparison to the AEs occurring during the study under the preferred term. An AE that occurs more than 30 days after the date of the last dose of investigational product in a treatment period will not be counted as a TEAE. For example, an AE occurs more than 30 days after the last dose in the initial treatment period, but before the first dose of any new acute AMR treatment period will not be counted as a TEAE.

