An overall summary of all AEs/TEAEs in each treatment group and/or treatment period will be presented respectively, including the number and percentage of subjects experiencing event, and absolute count of events with:

- Any AE/TEAE
- Any serious AE/ TEAE
- Any AE/TEAE related to investigational product in the opinion of the investigator
- Any AE/ TEAE leading to study drug discontinuation from the study
- Any severe AE/TEAE.
- Any AE/TEAE leading to death

The number and percentage of subjects and absolute count of events with AEs/TEAEs in each treatment group and/or treatment period will be tabulated respectively in the following ways:

- By SOC, preferred term
- By Maximum severity, SOC, and preferred term
- By SOC, preferred term for serious AE/TEAE
- By SOC and preferred term for AE/TEAE related to investigational product in the opinion of the investigator
- By SOC and preferred term for AE/TEAE leading to Death
- By SOC and preferred term for AE/TEAE leading to Study Drug Withdrawal

Total number of subjects on treatment for each treatment group will be given in all table headers.

For Serious AEs and AEs related to the investigational product, the table by SOC and preferred term will only be produced if there are greater than 5 events total. If there are less than or equal to 5 events, then only the listing will be provided.

All information about AEs collected on the CRF will be listed alongside the treatment, preferred term, and SOC.

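### Severity-split AE records: under SAP 11.1 a pre-dose event that only improves after dosing can be classed as treatment-emergent

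*Protocol*

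**What the plan says.** **Capture at the site.** Protocol 8.1.1 requires severity to be recorded through the course of an event, "including the start and stop dates for each change in severity", and adds that "An event that changes in severity should be captured as a new event". A separate sentence covers worsening of pre-treatment events, so the general rule is not confined to worsening.

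**Capture as the SAP describes it.** SAP 11.1 states that "An adverse event that increases in severity will be captured as a new event". Decreases are not mentioned.

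**TEAE definition (SAP 11.1).** An AE qualifies under either of two conditions.
- Condition 1: "it has a start date and time on or after the first dose of investigational product, or"
- Condition 2: the AE began before dosing "but increases in severity on or after the date and time of the first dose of investigational product"

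Two further rules follow. Where several AEs sharing a preferred term precede dosing, "then the AE with the greatest severity will be used as the benchmark for comparison to the AEs occurring during the study". And an onset later than 30 days after the last dose "in a treatment period will not be counted as a TEAE".

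**Reporting.** SAP 11.1 tabulates subjects (number and percentage), absolute event counts, and maximum severity. For serious and related AEs, "the table by SOC and preferred term will only be produced if there are greater than 5 events total"; otherwise only a listing is given.

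**The concern.** The SAP's definition works if a post-dose record means either a new event or a worse one. Under the protocol's capture rule it can also mean an older event getting better. Such a record has its own post-dose start date, so condition 1 accepts it.

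Pre-dose AEs can occur in this trial. They are collected from consent, and apheresis and IVIg may already be under way before study entry (Protocol 7.1.1). A TEAE table containing events that began before the drug and only improved misdescribes the drug's safety.

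The point survives the decision to stop the study. SAP Section 17 drops the key secondary, other secondary and exploratory efficacy analyses, but Section 20 keeps the TEAE tables (overall, by preferred term, by maximum severity, related, serious) for the abbreviated CSR.

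**Working it through.** The plan states no figure on this point, so there is nothing to reproduce. The check applies the written rules to illustrative severity paths of one clinical event.

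**Inputs**
- Protocol 8.1.1: any change in severity opens a dated record.
- SAP 11.1: a new record for increases only; conditions 1 and 2 joined by *or*; a benchmark for more than one pre-dose AE of the preferred term; a 30-day limit.
- Assumption: all changes fall within 30 days of the last dose of the treatment period.

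**Three readings**
- A: protocol capture, with condition 1 taken literally. TEAE events = number of post-dose records.
- B: the SAP's increase-only capture. TEAE events = post-dose onset, if any, plus post-dose increases.
- C: protocol capture, with every post-dose record compared with the worst pre-dose severity. TEAE events = post-dose records above that severity.

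| Path of one event | Records under protocol | TEAE events A / B / C | TEAE subject A / B / C |
|---|---|---|---|
| Severe pre-dose → moderate → mild | 3 | 2 / 0 / 0 | 1 / 0 / 0 |
| Moderate pre-dose → mild | 2 | 1 / 0 / 0 | 1 / 0 / 0 |
| Mild pre-dose → severe → mild | 3 | 2 / 1 / 1 | 1 / 1 / 1 |
| Post-dose onset: mild → moderate → severe → mild | 4 | 4 / 3 / 4 | 1 / 1 / 1 |

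**Does the benchmark prevent reading A?** In the first two paths only one AE of the preferred term precedes dosing. The benchmark is triggered by more than one, so by its own terms it does not apply. Where it does apply, the SAP does not say whether it limits condition 1.

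**Two separate effects**
1. *Classification.* In the two improving paths a subject who should contribute nothing becomes a TEAE subject (0 becomes 1). This affects both incidence and event counts.
2. *Multiple counting.* In the last two paths the subject is correctly counted once, but one event yields up to 4 event counts. This affects only the absolute event counts.

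The last row also shows that changing the protocol's wording to increases would not cure multiple counting: B still gives 3 events for one.

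**The case against.** The strongest reply is that SAP 11.1, read as a whole, already excludes improving events. It tests AEs by preferred term, says new records arise from increases, and sets the worst pre-dose severity as comparator. On that reading an event that began before dosing and never worsened falls under condition 2 and fails it. This is good evidence of intent, and no text says that condition 1 overrides the benchmark. But the text does not secure the intent: condition 1 has no severity test, the conditions are alternatives, and the benchmark omits the single pre-dose AE. A statement in the SAP about capture cannot change records that sites entered under the protocol.

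Several limits on the point stand in full:
- **Few events may qualify.** Screening lasts up to 7 days. Findings at the screening examination go to medical history unless clearly caused by an event after consent (Protocol 7.2.3.2), and AMR and expected disease symptoms are not AEs (8.1.5).
- **Overall TEAE incidence may hardly move.** In the pilot, 9 of 9 CINRYZE and 6 of 9 placebo subjects had a TEAE anyway (Protocol 1.3.2). Any effect would show mainly by preferred term.
- **The 5-event switch does little harm.** Two events of three records each give 2 × 3 = 6 and pass it, but passing it only adds a table.

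A reader might also infer that the DMC would see one resolving thrombosis as three. The documents do not support that. DMC outputs follow a separate DMC SAP that is not available here; clinically significant thrombotic events go by SAE form, with SAE onset and resolution generally tied to the serious criteria (Protocol 8.2.4, 8.2.6); and drug-related cases under the stopping rule are reviewed individually (Protocol 4.5.3).

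**Conclusion.** The defect is real and limited. The two documents disagree on when a new AE record is opened, and SAP 11.1 read literally then classes a single pre-dose event that only improves as treatment-emergent: 2 TEAEs and 1 subject in the severe-to-mild example, against 0 and 0. This rests on sites having followed Protocol 8.1.1 and on the step-down records starting within 30 days of the last dose of a treatment period.

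Two stronger readings should be avoided. Not every post-dose record becomes a TEAE, because of the 30-day limit. Nor can a rate of inflation, or of dilution between the arms, be given: the documents contain no severity-change data, and an assumed share of subjects, such as 10% to 30%, would be a guess. The correction should be made before the TEAE tables are produced, because a short rule removes a wrong classification from outputs that are still planned.

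**What to change.** In SAP 11.1:
1. Whenever one or more AEs of the same preferred term exist before the first dose, count a post-dose record that continues such an event as a TEAE only if its severity exceeds the greatest pre-dose severity. State that this overrides condition 1. A separate new episode stays under condition 1.
2. In the absolute event counts, including those used for the 5-event switch, count successive severity records of one event once, at maximum post-dose severity.

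In SAP Section 17, record that the protocol splits events on any change in severity while the SAP describes increases only. Rewording the protocol has little value now that the study has been discontinued, and would not stop worsening events from being split.

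Under these rules the four paths above give 0, 0, 1 and 1 TEAE events. All records stay in the listings, so no safety information is lost. The cost is a derivation rule, some programming, and data review to link records; the documents describe no linking field, so linkage would rest on preferred term, the start and stop dates of each severity step, and medical review. Reported event counts would be somewhat lower.

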8.1.2 Relationship Categorization

A physician/investigator must make the assessment of relationship to investigational product for each AE. The investigator should decide whether, in his or her medical judgment, there is a reasonable possibility that the event may have been caused by the investigational product. If there is no valid reason for suggesting a relationship, then the AE should be classified as “not related”. Otherwise, if there is any valid reason, even if undetermined or untested, for suspecting a possible cause-and-effect relationship between the investigational product and the occurrence of the AE, then the AE should be considered “related”. The causality assessment must be documented in the source document.

The following additional guidance may be helpful:

Term	Relationship Definition
Related	The temporal relationship between the event and the administration of the investigational product is compelling and/or follows a known or suspected response pattern to that product, and the event cannot be explained by the subject’s medical condition, other therapies, or accident.
Not Related	The event can be readily explained by other factors such as the subject’s underlying medical condition, concomitant therapy, or accident and no plausible temporal or biologic relationship exists between the investigational product and the event.

8.1.3 Outcome Categorization

The outcome of AEs must be recorded during the course of the study on the CRF. Outcomes are as follows:

- Fatal
- Not Recovered/Not Resolved
- Recovered/Resolved
- Recovered/Resolved With Sequelae

- Recovering/Resolving
- Unknown

8.1.4 Adverse Events of Special Interest

In addition, the following events of special interest, both serious and non-serious, will be closely monitored and reported to Shire PVRM via SAE form throughout the study, regardless of relationship to investigational product:

- Any thrombotic or thromboembolic event: thrombotic or thromboembolic events will be assessed for relatedness to investigational product. Stopping rules related to thrombotic or thromboembolic events are described in Section 4.5.3.
- Any hypersensitivity reaction
- Any new episode of kidney allograft rejection (excluding AMR)
- Kidney allograft failure as defined in Section 7.2.2.5

AESIs reported via SAE form that do not meet the serious criteria definition (Section 8.2.3) should be reported on the SAE form as being non-serious.

